RESPONSE: Skin integrity scales, change in ocular surface staining rating, participant comfort and satisfaction rating, and change in visual acuity. Skin integrity will be analyzed by applying a likert-type rating system to a high-mag/high-resolution photo documented image of the subject's lid skin. The number of adverse events will also be reported, defined as incidents which require temporary or permanent suspension of the participant's involvement. These include any broken skin, decrease in visual acuity more than 2 lines, worsening of corneal rating of more than 1.5 points or other ocular surface ratings more than 2 points, and comfort rating lower than 5/10 (or 50cm on the 100cm visual analog scale).

7b). Secondary Outcome(s) - Secondary outcome(s) are measures of additional or less important research interest. They may include additional clinical, psychological, economic, or safety outcomes (e.g. treatment related side effects/adverse events). However, as these endpoints are not used to calculate study power and sample size it is often not possible to draw robust conclusions from the results.

RESPONSE: Video analysis of eyelid biomechanics to measure the completeness of eye closure and opening compared to 1) no device, 2) relative to the contralateral side (if normal), 3) relative to the ptosis crutch or external lid weights. The same paired comparisons will be performed for the clinician and participant rating scale data. 3) Cognitive score on the MoCA will be analyzed for relationship to length of time in the study and satisfaction rating scores).

STUDY PROCEDURES

8) In this section you need to clearly and comprehensively describe exactly what will happen to participants once they are enrolled in your study. Depending on the study it might include how potential participants will be approached, when they will be randomized, the frequency and duration of visits or whether they are expected to self-complete a daily diary at home, the duration of the study or follow-up, and any measurements taken at each visit (e.g. questionnaires, physical measurements, biological samples).

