Next, a lid attached magnet array (see photos in manuscript attached) is painlessly applied to the upper lid with the participant's eye closed by placing a small swatch of Tegaderm medical adhesive (3M, St. Paul MN, Smith and Nephew, Canton MA) over the top of the micro-magnet array (a 1-minute procedure). For ptosis the array is only attached to the upper lid and a set of fit-over frames with a larger magnet embedded within the upper eye wire (spectacle magnet), which can be worn over the participants own glasses if needed, will be placed on and adjusted to the appropriate position. This secondary spectacle mounted magnet activates the ptosis system, providing the force to lift the lid. The spectacle magnet must be encased in plastic, and if the coating is too thin, the patient will not be able to blink properly. To determine the best coating thickness we will test 10 different coating thicknesses, done with 1mm plastic inserts which can be stacked. The video is recorded and rating instruments completed. This process is then repeated for lid magnets having a slightly modified polarity (thru height compared to the standard thru thickness). We will also test 4 different orientations of the spectacle magnet to determine the best fitting. **FOR LAGOPHTHALMOS** (failure of eye closure, e.g. facial palsy) the participant will first be fitted with a predicate device, an external lid weight, applied with double-sided "blink-eze" adhesive (supplied by the distributor with the product) and the video recording and rating instruments completed. Then this will be removed and lid magnet arrays identical (or very similar) to those described for ptosis will be applied to the upper and lower lids. The weight of the upper magnet will pull the eyelid down in a similar manner as the gold lid weight. (Townsend, 1992) The magnet on the lower lid will promote a more complete blink as the two magnet arrays draw towards one-another. A secondary

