spectacle mounted magnet may also be used for lagophthalmos (mounted within the inferior eye-wire to pull the upper lid down). In this scenario there is no lower lid array. **20 MINUTE TRIAL:** For both the ptosis and lagophthalmos magnet devices: If experimenter likert-type scale score is greater than or equal to 6 on the blink mechanics and efficacy and better than 8 on the skin integrity and the participant rated comfort is greater than or equal to 5/10 on likert-type or 50mm or better on a 100mm Visual Analog Scale and they express a desire to continue wearing the device, they will be offered participation in an extended 20 minute trial. This is followed by a repeat of the visual acuity, slit lamp exam, video and rating scale data collection. **EXTENDED 1-WEEK TRIAL:** Participants who have a successful 20 minute magnet device trial defined as an Examiner Rating Scale score of greater than or equal to 6 on the blink mechanics and efficacy, better than 8 on the skin integrity, participant rated comfort greater than or equal to 5/10 (or 50mm on a 100mm Visual Analog Scale), and express a desire to continue wearing the device will be offered participation in an extended 1-week trial. These cut-offs were based on observations during the pilot study at Spaulding (see manuscript attached) where patients who reported a desire to wear the device typically rated their comfort and satisfaction at this level or better. The PI or other trained study staff supervised by the PI will train the patient how to apply and remove the lid magnet; similar to what is done for insertion removal of contact lenses. They will be trained how to place on the secondary magnet spectacles to sit in the correct position on their face. If the participant is able to successfully demonstrate the ability to do this, only then will the magnet device be dispensed home with the patient (see exception* below). During each 1-week during the extended trial, the participant will be advised (instructional sheet sent with the participant) to wear the device as much as they would like up to 8 hours per day in the case of ptosis and 24 hours per day for lagophthalmos so long as comfort remains 5 or better (see participant instructions). Participants will be asked to document their wear time and assess their comfort on a 10-pt scale (10 being best) on a regular (min. daily) basis. For lagophthalmos, the device ideally will be worn 24 hours/day. For ptosis, the magnet glasses will be removed at night, and the lid magnet will remain attached to the eyelid. The participant may shower/wash face with the lid magnet on as the Tegaderm is not critically bothered by water and the magnet is encased in PDMS. They will be advised not to submerge the device (i.e. swim with the device on). Lid magnets will be removed and applied as they start to become detached (typically 2-3 days). If self-assessed comfort is worse than 5/10 or if the intervention fails (eg. stops working or falls off and cannot be reapplied) the participant will be instructed to contact the PI directly. The PI will advise if the device should be removed, and will come to MEEI or Schepens within 24 hours of the complication to evaluate the problem. If there is a problem requiring immediate attention, the participant will be advised to seek attention in the MEEI EW. **AT A 1-WEEK FOLLOW-UP** study appointment we will repeat visual acuity, slit lamp, rating instruments and video recording. **SAFETY CUTOFFS:** The participant's study status will change to suspended and an adverse event reported to the IRB with any of the following findings at the follow-up or any emergency visit: Any broken skin, decrease in visual acuity more than 2 lines, worsening of corneal rating of more than 1.5 points or other ocular surface ratings more than 2 points, and comfort rating lower than 5/10 (or 50cm on the 100cm visual analog scale). The extended trial of the magnet device may be renewed 3 times (for a total of 1 month with weekly visits) as long as the above mentioned criteria continue to be met. If still safe/effective at 1 month, the participant will be given the option to take the device home for an additional 1 month. The device trial/study ends after 8-weeks (4 weekly trials followed by a 1-month trial) or with failure/complication or voluntary withdrawal. If the device is successful over the duration of the study and the participant would like to continue wearing it, a clinical decision will be made as to if and for how long per day it should be worn. This is justified when there appears to be no other equivalent treatments which may be substituted. It would not be ethical to retract the device from a participant if it is working and there is no other comparable option. In such cases, the participant will return 1 month later for an additional follow-up evaluation prior to turning the maintenance of their care over to the neuro-ophthalmology, oculoplastics, or vision rehabilitation service. Their specialist will continue to monitor for complications after the study if the patient keeps the device. The study will end when 25 participants in each group have completed the study (~2yrs). **EXCEPTION* TO TRAINING REQUIREMENT:** If the participant is unable to apply and remove the device themselves (physical or cognitive limitations) and/or they have cognitive impairment (MMSE 20-23), they may still participate in an extended 1-week trial if the following criteria are met: 1) a caregiver is able to be trained to apply/remove the device, 2) The primary caregiver assures 24-hour supervision (see form on the last page of the "instructions for use document"), 3) The cognitively impaired participant (or participant who cannot apply the device themselves) agrees to attend daily study visits for the first

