
week of the extended trial. If there are no complications after 1-week, a clinical decision may be made by the PI to decrease the visit frequency to the standard protocol.

9) Randomization (if applicable)

Include the method (including any software) used to generate the random allocation sequence. Describe type of randomization performed, ratio of assignment to groups, block size permutation and stratification if applicable. Explain the methods used to conceal group allocation until assignment. Also, include information on who will generate the allocation sequence and who will assign participants into their groups.

This section should also discuss if participants, the investigator, and those assessing/analyzing the outcome(s) will be blind (or masked) to group assignment or if the study will be an open-label study (investigators and subjects know their assigned group).

RESPONSE: There is no randomization counterbalancing will be used given the small sample size.

10) Study Specific Procedures: List all procedures (interventions, tests, surveys, etc.) to be performed ONLY for research purposes

RESPONSE: Specific to the study are the high magnification photo analyses of skin integrity, participant comfort and satisfaction ratings (visual analog scales), video analyses of the eyelid movements to measure the change in the amount of eye-opening and closing (volitional and reflexive opening and closing) with the magnetic devices compared to no device, comparisons of the amount of opening and closing with the magnetic devices compared to with the ptosis crutch or external lid weights, and efficacy ratings by both the clinician and participant.

11) Standard of Care Procedures: Clearly list all standard of care (standard therapy) procedures (interventions, tests, etc.) to be performed regardless of the subject's enrollment in the study, but that will be included in the research assessment.

RESPONSE: NA

MEASUREMENT TOOLS

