13) Sample size and statistical power - A sample size or power calculation should be performed. This calculation is used to estimate the number of subjects required to answer your primary study hypothesis with an accepted power. Conversely, it also allows you to estimate what power can be achieved with a limited number of participants. This number is calculated by specifying the magnitude of the effects that are expected (i.e. informed and clinically significant), variability of the measurements and the acceptable degree of type I and II errors. You need to specify the assumptions made for the calculation. It is recommended that you consult with a statistician for this section. Also keep in mind the estimated recruitment rate and whether you need to adjust for anticipated non-responders and losses to follow up.

RESPONSE: The primary hypothesis is that externally mounted magnet systems will have a good safety profile and will be feasible for home use therefore we will report the proportion of participants who have a safety issue and complete the trial. As this outcome is based on summary statistics and not comparisons between groups, a power calculation is not appropriate. Sample size was selected based on providing an as-broad-as-possible but feasible (within the time of the study) assessment of safety and feasibility. The sample size calculation for the secondary within subject comparison between devices is estimated at 10 for the ptosis group, using preliminary unpublished data for cranial nerve III palsy at Spaulding (n=7; efficacy for opening (mm) magnet vs. crutch was borderline with 7 participants p=0.08, and comfort had reached significance, p=0.05). A power calculation is not possible for the lagophthalmos group as preliminary data are only available for 3 participants. Power calculations for the secondary analysis will be re-evaluated during data collection.

14) Statistical methods - The statistical methods used for the study objectives/hypotheses (e.g. t-test, chi-squared, multivariate modeling) must be sufficiently detailed. If conducting a randomized controlled study, you should state whether methods will include an “intention to treat” (ITT) analysis, per protocol analysis, or both. An ITT analysis is preferred as it compares all subjects in the

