groups to which they were originally randomly assigned (despite withdrawal, treatment failure or cross-over). Consultation with a statistician is strongly recommended. [See Harvard Catalyst Statistical Consulting for more information.](#)

RESPONSE: Descriptive statistics will be calculated including a mean rating scale value for skin, corneal integrity, and visual acuity (logmar). A repeated-measures ANOVA will be used to determine if there is any change across visits/measurements. The completeness of opening and closing with and without the magnet and with the other devices will be compared using paired t-tests. As this is not a randomized design, ITT will not be used.

DATA SAFETY MONITORING PLAN (DSMP)

Complete question 15 **OR** 16 depending on the risk of the study. If your study is submitted as minimal risk and determined by the HSC to be more than minimal risk you will be asked to complete question 16 during the review process.

15) If the research is **no more than minimal risk**, please describe any provisions in place to ensure the safety of participants and the validity and integrity of data. If safety monitoring will occur a safety monitoring plan may include elements such as: parameters for safety review, the frequency in which safety review will occur, the person(s) responsible for safety review, and the plan (including the person(s) responsible) for reporting adverse events, protocol deviations, or noncompliance to the HSC and others (where applicable). Data monitoring may include the specific elements that will be reviewed (e.g., informed consent documentation, verification of the accuracy of data), the frequency of data monitoring, and the person(s) responsible.

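### Section 8 fits the lid weight before the magnet in every lagophthalmos participant, so the secondary magnet-versus-weight comparison mixes device with order, and Section 9's mention of counterbalancing does not resolve it

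*Combined protocol and SAP*

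**What the plan says.** Section 8 (Study Procedures), in the lagophthalmos part of the device-fitting text, sets one order for everyone:

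- First device: "the participant will first be fitted with a predicate device, an external lid weight".
- Data taken with it: "and the video recording and rating instruments completed".
- Second device: "Then this will be removed and lid magnet arrays identical (or very similar) to those described for ptosis will be applied".

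No other order is described.

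Section 9 (Randomization) reads: "There is no randomization counterbalancing will be used given the small sample size". It names no factor, patient group or allocation scheme.

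Section 7b lists magnet versus external lid weight among the secondary outcomes for the video measures, and adds: "The same paired comparisons will be performed for the clinician and participant rating scale data". Section 14 says that opening and closing "with and without the magnet and with the other devices will be compared using paired t-tests". It specifies no period or sequence term. The repeated-measures ANOVA in the same section looks at change across visits or measurements and does not adjust this contrast for order.

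On numbers, Section 8 plans 25 participants per condition and also says: "The study will end when 25 participants in each group have completed the study". Section 13 says: "A power calculation is not possible for the lagophthalmos group as preliminary data are only available for 3 participants".

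**The concern.** When every participant has the weight first and the magnet second, device and position in the sequence are the same variable. Anything that changes between the first and second assessment is credited to, or charged against, the magnet.

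The procedures suggest several routes for such a change: repeated attempts at closure, adhesive already applied to and removed from the same upper lid, and ratings of the second device anchored on the first. The documents quantify none of these, and the net direction is unknown. The ratings are probably more exposed than the video measures, since Section 12 says that no validated instrument was available for comfort or efficacy.

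Section 9 may have been meant to prevent this. But staff work from the fitting sequence in Section 8, and the two sections cannot both be carried out if device order is what is counterbalanced. At stake is the study's only comparison of the magnet with the predicate device in lagophthalmos.

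**Working it through.** The plan gives no figure for this comparison, so there is none to reproduce. The first step is algebra; the rest is illustration under stated assumptions.

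**1. What the paired difference estimates.** Let δ be the true magnet-minus-weight effect and π the second-minus-first order effect.

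- Weight first: the expected difference is δ + π.
- Magnet first: the expected difference is δ − π.

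With everyone weight first, the mean difference estimates δ + π, and the data contain nothing that identifies π.

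**2. Inputs.**

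- n = 25 lagophthalmos participants (Section 8).
- n = 40 as an assumed larger case. The number fitted in the immediate trial may exceed 25 because the study ends on 25 completers per group.
- Assumed, because the documents do not give them: two-sided alpha 0.05, and π of 0.1, 0.2, 0.3 or 0.5 SD of the paired difference.

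**3. Fixed order, no device effect.** The paired t statistic is non-central t with n − 1 degrees of freedom and non-centrality π√n. For n = 25 and π = 0.3 this is 0.3 × 5 = 1.5 on 24 df, and the rejection rate is 30.2%.

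**4. Order counterbalanced 13/12.** The unadjusted mean keeps (13 − 12)/25 = 4% of π as bias. The period-adjusted estimate is the average of the two sequence means, with 13 + 12 − 2 = 23 df; π cancels. Rejection rates come from 400,000 simulated trials per setting.

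| Assumed π (SD) | Fixed order, n = 25 | Fixed order, n = 40 | 13/12, plain paired t | 13/12, period-adjusted |
|---|---|---|---|---|
| 0.1 | 7.7% | 9.5% | 4.8% | 4.9% |
| 0.2 | 16.1% | 23.5% | 4.6% | 5.0% |
| 0.3 | 30.2% | 45.7% | 4.1% | 5.0% |
| 0.5 | 67.0% | 86.9% | 3.0% | 5.0% |

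The plain paired t-test is slightly conservative under counterbalancing because an order effect of alternating sign inflates the SD of the differences.

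**5. Order effect in the opposite direction.** With δ = 0.5 SD and π = −0.2 SD under fixed order, the net effect is 0.5 − 0.2 = 0.3 SD. Power at n = 25 falls from 67.0% to 30.2%.

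**6. Price of the adjustment.** With δ = 0.5 SD and n = 25, power is 67.0% for the paired t-test without any order effect (24 df) and 66.7% for the period-adjusted test (23 df).

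**The case against.** **Section 9 may already commit to the remedy.** Device order is the natural reading of counterbalancing, and then only a wording conflict with Section 8 remains. This stands in part, and it is why the concern is conditional on Section 8 being followed. But no scheme is given, and the one operational description has a single order.

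**The Section 9 sentence lacks punctuation.** It could mean that neither randomization nor counterbalancing will be used, and a mark may have been lost in reading the PDF. On that reading the two sections agree, but the fixed order is then definite. If counterbalancing was meant only for the ptosis group, the lagophthalmos order is again fixed.

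**The comparison ranks low.** The secondary hypotheses in Section 4b concern the device against no device, and a comfort threshold. Magnet versus weight appears only in the Section 7b outcome list, and no power is claimed for it. This is correct and limits the weight of the point.

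**The sizes are hypothetical.** This is also correct. The rates show what follows if an order effect exists; they are not evidence that one does. The n = 40 case is only an example.

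**The plan does not say which magnet measurement is compared.** Magnet video and ratings are repeated after the 20-minute trial and at follow-up. Later measurements come from participants who passed the rating cut-offs, and alternating the immediate order would not correct for that selection or for wear time. This stands, and the fix must name the measurement.

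**Ptosis has a related gap.** Section 8 describes no crutch fitting, so the order for magnet versus crutch is undefined. That is fair, and the Section 9 clarification should cover both groups.

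**Conclusion.** The concern holds. Following Section 8 as written makes device and order inseparable in the lagophthalmos magnet-versus-weight comparison, and Section 9 does not resolve this on any reading of its sentence.

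The confounding follows from the text and needs no numerical assumption. Its size is unknown: the bias equals the whole order effect, in either direction. The rejection rates above depend on the assumed order effects, a two-sided 5% test and the immediate magnet assessment being the one compared.

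The consequence is confined to a secondary outcome; the primary safety and feasibility summaries and the hypotheses in Section 4b do not rest on it. It should still be changed, because fixed-order data cannot be repaired by later analysis.

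**What to change.** Reconcile Sections 8 and 9:

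- **Section 9:** state what is counterbalanced, in which group and by what scheme.
- **Section 8, if device order is meant:** rewrite the lagophthalmos step so that the order of the immediate weight and magnet assessments alternates by enrolment number or follows a pre-printed list.
- **Recording form:** add a column for the order actually used.
- **Section 14:** name the immediate magnet measurement as the one compared with the weight, and add a period term to the paired analysis. The term removes an order effect that is equal in both sequences. Unequal carry-over would remain and should be named as a limitation.
- **If the weight must stay first:** report magnet versus weight as a mean difference with a confidence interval and no p-value, and state that order is confounded with device.

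The cost is about one sentence in each of Sections 8, 9 and 14 and one column on the form. No extra visits, devices or staff are needed. The period term uses one degree of freedom.

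### A 20-minute acuity or corneal finding beyond the protocol's own cutoffs passes the gate to home use in item 8 but is an adverse event requiring suspension in item 7a

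*Combined protocol and SAP*

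**What the plan says.** Item 8 takes each participant through a fitting, a 20-minute trial and then a home trial renewed week by week. Acuity and an anterior segment examination with staining are recorded at baseline. After the 20 minutes of wear, item 8 states: "This is followed by a repeat of the visual acuity, slit lamp exam, video and rating scale data collection".

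The gate to the home trial follows: "Participants who have a successful 20 minute magnet device trial defined as an Examiner Rating Scale score of greater than or equal to 6" for blink mechanics and efficacy, together with a skin score better than 8, comfort of at least 5/10 and a wish to continue. The participant must then show that the device can be applied and removed, and "only then will the magnet device be dispensed home with the patient" (a caregiver exception is provided).

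The SAFETY CUTOFFS paragraph of item 8 comes directly after the 1-week follow-up. It requires suspension and an IRB report "with any of the following findings at the follow-up or any emergency visit". The findings include "decrease in visual acuity more than 2 lines, worsening of corneal rating of more than 1.5 points".

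Item 7a carries the same list. It introduces adverse events as "defined as incidents which require temporary or permanent suspension of" the participant's involvement, and sets no visit or time limit. Item 13 says that the proportion of participants with a safety issue will be reported, without a start point or denominator.

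**The concern.** The reading after 20 minutes is the only acuity and slit-lamp examination that item 8 schedules between first exposure to the device and home wear. The Background describes this as the first study to send participants home with the device, after earlier work in supervised inpatients wearing it up to 2 hours a day. Item 8 now allows up to 8 hours a day for ptosis and 24 for lagophthalmos. On the standard schedule the next planned acuity and slit-lamp examination is a week later.

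Two things are at stake. One is participant safety: the written gate does not look at two of the primary safety measures, although both have just been taken. The other is the endpoint: two people applying the protocol in good faith could give the same participant opposite status, and two analysts could put that participant in or out of the safety proportion.

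**Working it through.** The plan states no figure on this point, so the check is a comparison of the rules.

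| Measure | Gate after 20 minutes (item 8) | SAFETY CUTOFFS (item 8) | Adverse events (item 7a) |
|---|---|---|---|
| Blink mechanics, efficacy | at least 6 | none | none |
| Skin | better than 8 | any broken skin | any broken skin |
| Comfort | at least 5/10 | below 5/10 | below 5/10 |
| Visual acuity | none | loss of more than 2 lines | loss of more than 2 lines |
| Corneal rating | none | worse by more than 1.5 points | worse by more than 1.5 points |
| Other ocular surface ratings | none | worse by more than 2 points | worse by more than 2 points |
| Visits covered | after the 20-minute trial | follow-up or emergency visit | not limited |

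Skin and comfort appear in all three columns. Acuity and the ocular surface ratings are missing from the gate alone.

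**Test case.** Suppose that after 20 minutes a participant has lost 3 lines of acuity, or the corneal rating is 2 points worse, while blink mechanics and efficacy score 6 or more, skin is better than 8, comfort is at least 5/10 and the participant wishes to continue.

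1. Gate in item 8: every listed criterion is met, so the trial is successful and the home trial is offered.
2. SAFETY CUTOFFS in item 8: 3 > 2 lines and 2 > 1.5 points, so the finding is beyond the cutoff, but this visit is not named. The same finding at the 1-week follow-up means suspension and an IRB report.
3. Item 7a: the finding is on the list and no visit is excluded, so it is an adverse event requiring suspension.
4. Item 13: nothing says whether findings before dispensing enter the proportion.

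Steps 1 and 3 conflict. Item 7a does not settle the matter, because it depends on an incident requiring suspension, and the only operational suspension rule is the one in step 2.

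**Scale per case.** No event rate is given, so this is arithmetic on one assumed case, with exact (Clopper-Pearson) 95% intervals:

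- Group of 25: counted, 1/25 = 4.0% (0.1% to 20.4%); not counted, 0/25 = 0% (0% to 13.7%).
- All 50: counted, 1/50 = 2.0% (0.1% to 10.6%); not counted, 0/50 = 0% (0% to 7.1%).

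For zero events the upper limit is 1 − 0.025^(1/n): 1 − 0.025^(1/25) = 0.137 and 1 − 0.025^(1/50) = 0.071.

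**The case against.** The strongest reply is that item 8 should not be read alone. Item 7a lists these findings as adverse events with no visit limit and ties them to suspension, and a suspended participant would not be sent home with the device. Item 15 provides for on-site monitoring by staff experienced in eye examination, who can act at once, and for an event log not tied to particular visits. Item 14 reports mean corneal and acuity values and tests change across visits, and nothing there excludes the 20-minute readings.

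Most of this stands, and it rules out several stronger readings that a reader might infer:

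- That early ocular harm does not count as an event. Item 7a says otherwise.
- That acuity and slit-lamp results are measured and then ignored. They are absent from the gate, but not from the analysis plan.
- That the safety proportion begins only after dispensing and so leans towards safe. Item 13 sets no start point in either direction.
- That acuity and cornea are missing from the safety cutoffs. Both are there; only this visit is not named.

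What the reply does not remove is the conflict. The gate is stated as a definition, it is the rule staff would apply on the day, and it passes the test case. Item 7a can be set against it, but no passage says which prevails.

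**Conclusion.** The concern holds as a contradiction within the protocol. For an acuity or corneal finding beyond the stated cutoffs after the 20-minute trial, the item 8 gate leads to an offer of home use and item 7a leads to suspension with an adverse event. Whether the case enters the item 13 proportion is open to either reading.

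It goes beyond missing detail, because followed as written the gate admits to first unsupervised wear a participant whose identical finding a week later would mean suspension.

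No overall size can be given, since the documents report no rate of such findings at 20 minutes. The per-case shift of 4.0 percentage points in 25, or 2.0 in 50, assumes one event and those denominators. A reader might infer that events are being lost and the endpoint biased; the documents do not show this.

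The conclusion rests on reading the follow-up in the cutoffs as the home-trial follow-up, which the sentence just before it supports.

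**What to change.** Reconcile three passages: the definition of a successful 20-minute trial and the SAFETY CUTOFFS in item 8, and the adverse-event definition in item 7a. The protocol should then state how an acuity or corneal finding after 20 minutes, beyond its own cutoffs, bears on going on to home use. The clinical rule is for the sponsor to decide.

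For the endpoint, state in items 7a and 13 that the event thresholds are assessed on the 20-minute readings, and that participants who meet them count in the proportion with a safety issue.

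The cost is wording. No new measurement should be needed: acuity and slit lamp are already repeated at that point, and item 8 uses the same slit-lamp term for the 1-week visit, where the corneal cutoff applies. The thresholds are already written. The downside is that the reported event proportion may rise slightly.
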